Our research group has previously initiated a prospective study including kidney transplant candidates older than 65 years who are listed for transplantation at Oslo University Hospital, Rikshospitalet (QUESTION65). At present, 289 patients are included and 214 have been transplanted. Results have been presented at top international conferences (ERA-EDTA, ASN, ESOT, ATC). The first PhD protocol using data from this study was started in 2015 (PhD student [name]) the protocol focusing on short- and intermediate-term changes in HRQoL, effect of comorbidity on short-term complications and HRQoL and a qualitative evaluation of the patients' expectations.

For patients with end stage renal disease (ESRD), kidney transplantation is in general considered as the best treatment-option both with respect to survival (1), costs (2, 3) and HRQoL (4). Selected older patients have also been shown to improve survival after transplantation compared to dialysis (5, 6). For decades Oslo University Hospital, Rikshospitalet has been Europe's largest kidney transplantation center.

As a result of the general aging of the population, the number of older individuals with chronic diseases including chronic kidney disease is expected to increase significantly over the next 25 years. Consequently, the number of older kidney transplant candidates will also increase. Contrary to most other countries in the world, Norway has never had any upper age limit for kidney transplantation. In spite of this, we have had among the shortest waiting-time worldwide (7). Due to organ scarcity, transplant centers often have an upper formal or practical age limit for potential recipients. In some countries patients older than 50-55 years may end up spending the rest of their life in hemodialysis. The major challenge concerning allocation of donor organs is to find those patients who will derive the most benefit of transplantation in terms of improved patient outcome, less complications and increased survival time. Today, most centers use the same medical criteria for all patients, regardless of age. Based on the literature there is, however, a knowledge gap between what is documented for older patients versus younger patients.

Most data describing HRQoL after kidney transplantation have been collected from adult populations (median age ~ 50 years) (4, 8). Information on if/how HRQoL of older ESRD patients change during different phases of the treatment (dialysis, early post transplantation and long term transplantation) is very sparse (4) and for older patients the documentation is restricted to small cross sectional studies comparing a group of older recipients with either older patients on dialysis treatment or younger transplant recipients (9, 10). To our knowledge, no prospective study describing HRQoL longitudinally in older patients from pre-transplant through the immediate, short term and long-term phases post-transplant has been published. In 2018, RN [name] defended her PhD thesis on basis on the QUESTION65 study describing the short term HRQoL effects of kidney transplantation in the elderly (11-13). Consequently, there is a knowledge gap concerning how kidney transplantation affects HRQoL in the long term compared to the alternative; lifelong dialysis treatment.

Date of Update: April 5. 2020

Older patients with ESRD often have a high burden of co morbidities. The most widely used comorbidity index is the Charlson comorbidity index (CCI) (14). The CCI has been validated in several populations including patients with ESRD (15). In recipients older than 70 years, the CCI has, however, not been shown to be associated with survival after kidney transplantation (16). More recently, other comorbidity scores have been developed for patients with ESRD (17, 18). However, these indexes are not validated in the elderly. We are consequently lacking instruments validated in older transplant candidates for standardized measurement of comorbidity.

Even though kidney transplantation is regarded as the most cost-effective treatment of ESRD, to our knowledge no proper health economic evaluation of transplantation in older patients exists.

2.1 Added value of the project

Added value for the patients: Increased knowledge of the outcomes after kidney transplantation will be important for the patient's choice of treatment. The findings will provide the patients and their families comfort and knowledge that timely specialist evaluation can help improve outcomes and reduce symptoms in older people with advanced kidney disease – whether they have selected conservative management, dialysis or kidney transplantation as their treatment plan. Improved selection criteria for transplantation will improve the patient outcomes by selecting the correct patient for the correct treatment.

Added value for the health service: The project will provide novel information that the clinicians can use to utilize the limited donor organ resources in an optimal way. The situation for kidney transplantation in Norway is currently changing. For the last decade we have had a stable situation with approximately 200 patients on the transplantation waiting list and a mean waiting-time of 9-12 months. Over the last years, the number of waitlisted patients has however increased significantly and consequently the waiting-time for kidney transplantation has become markedly longer. This situation has already resulted in some discussion on whether we should change our selection-criteria for including patients on the waiting list. One possibility is to set an upper age limit for potential kidney transplant recipients.

Our research group will argue that it is important not to set an upper age limit but rather improve the selection criteria for elderly kidney transplant candidates. The challenge is to improve the selection of recipients expected to go through the post-operative phase without major complications and thus being the ones most likely to profit from kidney transplantation.

We hypothesize that selection criteria of elderly recipients with ESRD can be improved by combining data from a pre-transplant comorbidity score and self-reported health related quality of life (HRQoL). We believe our research will improve the individual evaluation of each patient and provide each patient with the best treatment option available, both with respect to survival and quality of life. By identifying patients who will *not* benefit from transplantation, the organ can be allocated to another patient on the waiting list, thereby reducing the waiting time. The findings will be of strategic importance for future treatment of all patients in Norway with ESRD, regardless of age.

Added value for the society: Improved selection criteria combined with health economic evaluation will provide important guidance in the search for cost-effective treatment algorithms which is necessary if we should be able to utilize our health budget optimally. Evidence of the cost-effectiveness of various treatment options is required to facilitate appropriate resource planning and develop optimal treatment models across diverse health care settings. Policymakers need evidence that an intervention or program of care represents the most efficient use of available resources and

Date of Update: April 5, 2020

provides value for money. Health economic evaluation is a systematic way of producing this evidence (19).

3. Aims

The overall aim of this study is to collect and evaluate long-term data on patient reported, clinical and health economic outcomes following kidney transplantation in older patients (≥ 65 years of age at enlisting). Further specific aims are:

Aim 1:

To evaluate patient reported HRQoL longitudinally from time of wait listing and up to 5 years after transplantation in kidney transplant candidates older than 65 years of age.

These data will describe if and how patient reported HRQoL changes over time and thereby evaluate whether the benefit of transplantation described for general adult patients is also valid for older recipients. The data will also make it possible to compare the effect on HRQoL and clinical outcomes for patients on long-term dialysis compared to patients several years after transplantation.

Aim 2:

To investigate the relationship between pre-transplant comorbidity, expressed as the Liu comorbidity index and post-transplant HRQoL at 1-3 years post transplant.

Detection of any association between pre-transplant comorbidity and post-transplant HRQoL, can improve the selection process of older transplant candidates by including the comorbidity score as part of the patient selection algorithm.

Aim 3:

To investigate the relationship between pre-transplant comorbidity, expressed as the Liu comorbidity index, pre-transplant HRQoL described by KDQOL-SF and post-transplant patient- and graft survival.

Aim 4:

To evaluate kidney transplantation in older patients in a health economic perspective, including evaluation of quality adjusted life years (QALY), and investigate if QALY values are changing over time. By collecting standard cost estimates for the different procedures, we should be able to calculate an incremental cost-effectiveness ratio (ICER) for kidney transplantation versus dialysis

This aim will provide further information about the benefits kidney transplantation can or cannot provide older patients from a health economic perspective. This analysis will be of major importance for present and future priority discussions.

4. Implementation

Data will be retrieved from the QUESTION65 database described previously, and the Norwegian Renal Registry. Missing data will be retrieved from the patient records at Oslo University Hospital, Rikshospitalet and from the patients' local hospital records. The key necessary for identification of patients will be stored at the registry and will not be available for the researchers.

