4.1. Design, methods and analyses

Statistics

All statistical analyses will be performed using the statistical software package SPSS Statistics version 22 or later. Scores from KDQOL-SF will be calculated and compared using traditional statistical methods (two-sided unpaired t-test or paired t-test, ANOVA, logistic regression). Fisher's exact test will be used to analyze binary data. Other standard statistical methods as for example multiple variable logistic regression analyses will be used as needed. Survival analyses will be performed using the Kaplan-Meier method and Cox proportional hazard models.

Aim 1:

Data collection: Patient reported outcomes are collected in an on-going, prospective, longitudinal study (QUESTION65). By the end of inclusions in December 2016, we estimate that 280 patients should be included. All patients give their written informed consent before inclusion in the study. In addition, all patients have signed an informed consent when they were included in the Norwegian Renal Registry. This allows the use of unidentified data from the registry in research protocols.

HRQoL is assessed using the KDQOL-SF-36 health Survey (20, 21). This survey consists of two parts, a generic (SF-36) and disease specific (KDQOL) part. The same questionnaire is used before and after transplantation. The results will also be compared with data from an age matched Norwegian cohort (22).

All patients over the age of 65 years, who are accepted for the kidney transplantation waiting list or living donor transplantation, receive an invitation to participate in the study. In addition to provide baseline data, all patients receive additional forms with the same questionnaires every sixth months until they are transplanted, permanently removed from the transplant waiting list or deceased. Patients who are transplanted will receive a discharge form from Rikshospitalet (10 weeks after transplantation), after six months and at one-, three-, five-, seven- and ten years post-transplant.

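### Aim 2 relates the Liu index only to the HRQoL level after transplantation, which is prognosis; it does not show who gains less or what Liu adds to pre-transplant HRQoL, yet any association is offered as grounds for selection

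*Combined protocol and SAP*

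**What the plan says.** Section 3 states Aim 2 as: "To investigate the relationship between pre-transplant comorbidity, expressed as the Liu comorbidity index and post-transplant HRQoL at 1-3 years post transplant". The Aim 2 data paragraph in section 4.1 names post-transplant HRQoL values and no pre-transplant ones. Directly after the aim, section 3 gives the intended use: "Detection of any association between pre-transplant comorbidity and post-transplant HRQoL, can improve the selection process of older transplant candidates", by making the score part of the selection algorithm.

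Section 2.1 says what selection is for. Its hypothesis is that selection can be improved by "combining data from a pre-transplant comorbidity score and self-reported health related quality of life (HRQoL". It also says that once patients are identified who will not "benefit from transplantation, the organ can be allocated to another patient on the waiting list".

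Aim 3 does bring the two predictors together, but its outcome is survival: it relates the Liu index to "pre-transplant HRQoL described by KDQOL-SF and post-transplant patient- and graft survival". Aim 1 describes HRQoL over time without the Liu index.

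The Statistics paragraph of section 4.1 is general and ties no method to Aim 2: "Scores from KDQOL-SF will be calculated and compared using traditional statistical methods (two-sided unpaired t-test or paired t-test, ANOVA, logistic regression". It adds that other standard methods may be used as needed. The same questionnaire is given before and after transplantation.

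**The concern.** Two different questions sit behind the selection sentence. One is prognostic: do recipients with a higher Liu index have lower HRQoL later? The other concerns gain: do they improve less? Aim 2 as written answers the first. If candidates with a higher index start lower and improve as much as the rest, Liu will still be associated with the later level. That finding could then be cited for counting comorbidity in the selection algorithm, although nothing has been shown about gain.

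The combining hypothesis is also left open for HRQoL as an outcome. Without the baseline score in the model, the analysis cannot show whether Liu carries information beyond what the candidate's own pre-transplant score already gives. Aim 3 covers that combination for survival only.

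**Working it through.** **The plan's own figure.** Section 4.1 gives 63 patients for Aim 1 and a similar number for Aim 2. With GH 50 against 40, SD 20 (assumed; the midpoint of the stated 15 to 25), two-sided 5% and 80% power:

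n = 2 × 20² × (1.960 + 0.842)² / 10² = 62.8, so 63 per group.

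The figure reproduces. It is a comparison of two means and contains no Liu effect or correlation, so it says nothing about the size of the Aim 2 question.

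**Inputs for the illustration.** GH SD of 15 to 25 comes from section 4.1. N = 214 comes from the background ("289 patients are included and 214 have been transplanted"). It is a round working size: deaths and unreturned forms reduce it, and further transplants could add to it. The Liu-baseline correlation r is an assumption. Gain is set equal at every Liu level throughout.

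**Model A: gain independent of baseline, SD 15 before and 25 after.**
- corr(Liu, post) = r × 15/25. At r = -0.2 this is -0.12.
- Level slope: -0.2 × 15 = -3.0 GH points per SD of Liu.
- Liu adds nothing beyond baseline, and the change slope is 0.

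**Model B: equal SDs of 20.**
- corr(Liu, post) = r = -0.2.
- Level slope: -0.2 × 20 = -4.0 points per SD of Liu; the change slope is 0.
- The baseline-adjusted slope is SD × r(1 - ρ)/(1 - r²), where ρ is the pre-post correlation. At ρ = 0.5 it is 20 × (-0.2) × 0.5/0.96 = -2.1, so Liu still adds prognostic information.

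**Chance of detecting the level association.** Power = Φ(|atanh(corr)| × √(N - 3) - 1.96), plus a negligible opposite tail except at r = 0, with √211 = 14.53.
- r = 0: 5%.
- Model A, r = -0.2: 0.1206 × 14.53 - 1.96 = -0.21, giving 42%.
- Model B, r = -0.2: 0.2027 × 14.53 - 1.96 = 0.98, giving 84%.

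The test of Liu against change rejects in about 5% in both models. In simulation the baseline-adjusted test rejected in about 41% under Model B (r = -0.2, ρ = 0.5, N = 214) and about 5% under Model A (5.6%, run at r = -0.3). The two analyses therefore answer different questions and cannot replace each other.

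**Precision of the change analysis.** The 95% CI half-width per SD of Liu is 1.96 × SD × √(2(1 - ρ))/√N. With SD 20 and ρ from 0.6 to 0.4 (assumed):
- N = 214: 1.96 × 20 × (0.894 to 1.095)/14.63 = 2.4 to 2.9 points.
- N = 63: 1.96 × 20 × (0.894 to 1.095)/7.94 = 4.4 to 5.4 points.

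Comparing +1 SD with -1 SD of Liu doubles these. At N = 63 that is 8.8 to 10.8 points, about the 10-point difference in the plan's own sample-size calculation.

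**The case against.** The strongest reply is that nothing is wrong with Aim 2 as an association study. Expected HRQoL after transplantation is a legitimate thing to know about a candidate, and section 2.1 itself mentions both survival and quality of life. The tentative paper in section 4.4 is titled as an association. The selection sentence says an association can improve selection; it is a rationale, not a decision rule. All of this stands. What remains is that the sentence accepts any association, and a level association alone does not reach the gain question.

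The methods list also leaves room. ANOVA could cover a comparison of Liu groups over time, an unpaired t-test could be applied to change scores, and other methods may be used as needed. A reader might infer that the plan rules out a baseline-adjusted or change analysis. It does not; it only fails to commit to one. The paired t-test, taken alone, tests mean change and not whether change varies with Liu.

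A reader might also take section 2.1's phrase about candidates "thus being the ones most likely to profit from kidney transplantation" as defining benefit by HRQoL gain. In its sentence that phrase is tied to coming through the post-operative phase without major complications, so it does not carry that weight. The case rests on the sentence about patients who will not benefit, which does not define benefit as HRQoL change either.

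Finally, every detection percentage depends on an assumed r, and at r = 0 the difficulty disappears. The documents do not say that candidates with a higher index start lower or gain as much. That also stands, which is why the percentages are illustration only.

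**Conclusion.** The point holds as a mismatch between what Aim 2 names and the use announced for it. The plan names a prognostic association, commits to no analysis of differing gain or of Liu's contribution beyond baseline HRQoL, and says any association can support selection.

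The size cannot be fixed from the documents. Under equal gain, N = 214 and r = -0.2, the level association would be found in about 42% of studies when Liu adds nothing beyond baseline (Model A), and in about 84% when it still does (Model B). A reader might take the 84% as a false-positive rate, or as the chance of an association that merely carries forward a low start. Neither is supported: the association is real in both models, and in Model B Liu still predicts the later score among patients with the same baseline.

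Nor would a change analysis show benefit over dialysis. Aim 2 contains only recipients, and only those alive who returned a form.

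This is a worthwhile and cheap clarification, not an invalid analysis. I did not have the text between the Aim 4 power statement and section 4.3, so a commitment made there would change the conclusion.

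**What to change.** Using the pre-transplant questionnaires already collected, pre-specify for Aim 2, for GH (the dimension named as primary under Aim 1) at one named primary time point:

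1. Regression of post-transplant GH on the Liu index with the last pre-transplant GH as covariate, as the analysis of whether Liu adds prognostic information.
2. The association of Liu with change in GH from the last pre-transplant score, with its 95% CI, as the analysis used for any statement about differing gain. Read it from the interval, not from a non-significant p-value.
3. New wording for the sentence after Aim 2 in section 3, so that an unadjusted association with the post-transplant level does not by itself support a selection statement. Describe Aim 2 as prognosis among surviving recipients who returned forms, not as benefit over dialysis.

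The cost is two regression models and some wording, with no new data collection. There are two drawbacks. Recipients without a pre-transplant form must be dropped or imputed. The change analysis is also imprecise, so with numbers near 63 a null result could not be read as equal gain.

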4.1. Design, methods and analyses

Statistics

All statistical analyses will be performed using the statistical software package SPSS Statistics version 22 or later. Scores from KDQOL-SF will be calculated and compared using traditional statistical methods (two-sided unpaired t-test or paired t-test, ANOVA, logistic regression). Fisher's exact test will be used to analyze binary data. Other standard statistical methods as for example multiple variable logistic regression analyses will be used as needed. Survival analyses will be performed using the Kaplan-Meier method and Cox proportional hazard models.

Aim 1:

Data collection: Patient reported outcomes are collected in an on-going, prospective, longitudinal study (QUESTION65). By the end of inclusions in December 2016, we estimate that 280 patients should be included. All patients give their written informed consent before inclusion in the study. In addition, all patients have signed an informed consent when they were included in the Norwegian Renal Registry. This allows the use of unidentified data from the registry in research protocols.

HRQoL is assessed using the KDQOL-SF-36 health Survey (20, 21). This survey consists of two parts, a generic (SF-36) and disease specific (KDQOL) part. The same questionnaire is used before and after transplantation. The results will also be compared with data from an age matched Norwegian cohort (22).

All patients over the age of 65 years, who are accepted for the kidney transplantation waiting list or living donor transplantation, receive an invitation to participate in the study. In addition to provide baseline data, all patients receive additional forms with the same questionnaires every sixth months until they are transplanted, permanently removed from the transplant waiting list or deceased. Patients who are transplanted will receive a discharge form from Rikshospitalet (10 weeks after transplantation), after six months and at one-, three-, five-, seven- and ten years post-transplant.

Statistical power: The primary objective of the study is to detect differences in the QOL dimension general health (GH). According to the literature, SF-36 scores for GH varies between 47 and 69 for transplanted patients and between 36 and 44 for patients treated in haemodialysis (10, 23, 24). The standard deviation in these studies varies between 15 and 25. A clinically significant difference in SF-36 GH score is estimated to be around 10%. With a predicted SF-36 GH score of 50 for transplanted patients and 40 for patients in haemodialysis, we need a minimum of 63 patients to complete the study to reach a significance level (α) of 5% and a power (β) of 80%. According to previous analyses, 80% of patients > 70 years who are accepted for the kidney transplantation wait list will eventually be transplanted and five year survival in this age group is 64% (5). Consequently, a minimum of 100 patients must be transplanted and hence, an even higher number must be included at baseline. To have the possibility to evaluate the impact of gender and dialysis modality, the number of included patients has been further increased up to a total of 280. The regional committee of medical and health research ethics have approved this increase.

By August 2016, 261 patients are included, 152 are transplanted. Consequently, the number included and transplanted patients are already well above the minimum number.

Aim 2:

Data collection: From 2012 we have included pre-transplant data according to the Liu comorbidity index (17) as part of the routine work up of candidates for kidney transplantation. Complete data describing patient and transplant characteristics, including the Liu comorbidity index will be

Date of Update: April 5. 2020

extracted from the Norwegian Renal Registry. The data will be exported from the registry without any identification except from a patient number. Post-transplant HRQoL values will be retrieved from the QUESTION65 database.

Statistical power: No previous studies describing the correlation between pre-transplant comorbidity and post-transplant HRQoL exist. Based on the same considerations as described for Aim 1, a similar number of patients should be necessary for Aim 2 to reach a significance level of 5% and a power of 80%.

Aim 3:

Data collection: Complete data describing patient and transplant characteristics, including the Liu comorbidity index will be extracted from the Norwegian Renal Registry as described for Aim 2. Pre-transplant HRQoL will be retrieved from the QUESTION65 database. Post-transplant survival data will be extracted from the Norwegian Renal Registry. The data will be exported from the registry without any identification except from a patient number.

Statistical power: No previous studies describing the correlation between pre-transplant comorbidity, pre-transplant HRQoL and post-transplant survival exist. Based on previous analyses on similar patient cohorts (25), 150 patients should be sufficient to detect statistically significant associations.

Aim 4:

Data collection: QALYs will be calculated from the SF-36 (SF-6D) scores available in the QUESTION65 database. From the SF-6D, a health index can be calculated. Patients who die during follow-up will have health index = 0 from time of death, and with this health index, QALYs can be calculated for each patient during follow-up. Costs necessary for estimation of cost/QALY and ICER will be estimated through use of information from the patient records at the patients' local hospitals as well as Oslo University Hospital. DRG weighted costs will be used for each contact (in-patient, out-patient and dialysis). In addition, medication costs will be estimated based on each patient's medication list and travel costs will be estimated based on the distance between the patient's home and the hospital.

Statistical power: No previous studies evaluating QALY in older kidney transplant recipients exist. Power calculation is therefore difficult to perform.

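### Aim 1 measures HRQoL repeatedly to five years, but the tests named for the scores include no longitudinal model, and each listed option handles death and unreturned forms differently

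*Combined protocol and SAP*

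**What the plan says.** Section 3 states Aim 1 as: "To evaluate patient reported HRQoL longitudinally from time of wait listing and up to 5 years after transplantation". Section 4.1 (Aim 1, Data collection) adds that "The same questionnaire is used before and after transplantation". Forms come every six months while the patient waits ("In addition to provide baseline data, all patients receive additional forms with the same questionnaires every sixth months"), then at 10 weeks, and "after six months and at one-, three-, five-, seven- and ten years post-transplant". Up to five years, a recipient can therefore have six main scores: baseline, 10 weeks, 6 months, and 1, 3 and 5 years.

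For KDQOL-SF scores, the Statistics paragraph of section 4.1 says they will be "compared using traditional statistical methods (two-sided unpaired t-test or paired t-test, ANOVA, logistic regression". It then leaves the list open: "Other standard statistical methods as for example multiple variable logistic regression analyses will be used as needed". The type of ANOVA is not given. Kaplan-Meier and Cox methods are named, but for survival.

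Two comparisons between people are also planned. One is dialysis versus transplanted patients (section 3, Aim 1; section 4.1, Aim 1 power). The other is a population norm: "The results will also be compared with data from an age matched Norwegian cohort".

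Two statements elsewhere come close to the question of missing scores. Section 4 says that missing data will be fetched from hospital records. Aim 4 sets the health index to 0 from death, for QALYs. Neither says how a general health (GH) score is analysed after death or when a form is not returned. Part of section 4, between Aim 4 and the budget, was not available for this review.

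**The concern.** GH is the primary variable, and the aim is change over time in a group in which many die. The listed tests answer different questions about different patients:

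- A paired t-test uses patients with both forms.
- Classical repeated-measures ANOVA uses patients with every form.
- An unpaired test or one-way ANOVA across visits sets everyone at baseline against those who survive and respond later. It then counts selective survival as improvement.

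None of them uses the intermediate scores of a patient who missed one form. Hospital records cannot be expected to supply a self-report that was never returned. At stake are which patients the five-year change describes, how precise it is and, under one permitted use, whether it is biased.

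**Working it through.** **The plan's own figure.** Section 4.1 (Aim 1, power) says "we need a minimum of 63 patients to complete the study", for GH 50 versus 40, two-sided 5%, 80% power. At SD 20 (assumed; midpoint of the stated 15-25), an unpaired comparison needs 2 × (1.96 + 0.84)² × 20² / 10² = 62.8, so 63 per group. Also 63 / 0.64 = 98.4, in line with the stated 100 transplanted. The figure thus fits an unpaired between-group test. For paired change at within-patient correlation 0.5 (assumed), 32 pairs would do.

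**Patients available at year 5.** Inputs: 214 transplanted (background section) and 64% five-year survival (section 4.1, a figure for patients over 70). Assumed: 85% form return; the plan gives no rate.

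- Alive: 214 × 0.64 = 137.
- Both baseline and year-5 forms: 137 × 0.85² = 99, or 137 × 0.85 = 116 if baseline is complete.
- All six forms, returned independently: 137 × 0.85⁶ = 52, or 137 × 0.85⁵ = 61 if baseline is complete.
- All six forms, with return clustering within patients (beta-binomial, mean 0.85, intra-patient correlation r). The probability of k returned forms is the product over i = 0 to k−1 of (0.85s + i)/(s + i), with s = 1/r − 1. At r = 0.1 and k = 6 it is 0.4635, giving about 64. At r = 0.3 and k = 5 (baseline complete) it is 0.617, giving 85. The range is about 64-85.

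**Bias and precision.** Simulation of 214 recipients. Assumed: SD 20, correlation 0.5 (random intercept), 85% return, a true change of 5.0 in everyone, and a death hazard 1.5 or 2.0 times higher per SD lower patient-mean GH, calibrated to 64% five-year survival.

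| Year-5 estimate (truth 5.0) | Hazard ratio 1.5 | Hazard ratio 2.0 |
|---|---|---|
| Unpaired, across visits | 7.5 | 9.0 |
| Paired t-test | 5.0 | 5.1 |
| Mixed model, alive at year 5 | 5.0 | 5.1 |
| Mixed model, all recipients | 5.6 | 6.1 |

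The unpaired excess is 2.5 and 4.0 points at year 5. It is 1.5 and 2.5 at year 3, and 0.5 and 0.9 at year 1. At an assumed 80% survival, the year-5 excess is 1.3 and 2.1. At hazard ratio 2.0 and 64% survival, SD 15 or 25 gives 3.0 or 5.0. With death unrelated to GH there is none.

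The unpaired excess can be checked without simulation. It is 20 × √0.5 = 14.1 times the mean standardised GH of survivors, and numerical integration gives 2.5 and 3.9 at year 5.

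Standard errors at year 5, with baseline 85% / complete:

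- Complete-case ANOVA: 2.81-2.88 / 2.55-2.63.
- Paired: 2.01 / 1.86 (check: 20/√99 = 2.01; 20/√116 = 1.86).
- Mixed model among the living: 1.89-1.90 / 1.80-1.82.

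Variance ratios, from mid-range standard errors:

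- Against complete-case ANOVA: (1.895/2.845)² = 0.44 and (1.81/2.59)² = 0.49, about half.
- Against paired: (1.895/2.01)² = 0.89 and (1.81/1.86)² = 0.95. Over the range this is 4-12% less.

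**Sensitivity.** Baseline complete, hazard ratio 1.5, odds of return 1.5 or 2.0 times lower per SD lower patient mean. The survivors' model gives 5.23 or 5.35 and the paired test 5.08 in both, with equal root mean square error (1.81 and 1.82).

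**The case against.** The strongest reply is that the plan already lists the paired t-test, that anyone analysing within-patient change would choose it, and that it is unbiased for survivors' change here. Against it, a mixed model offers little precision and can itself be slightly off when return depends on health. The open clause in section 4.1 also permits such a model. This stands, and it limits the point to a modest improvement and a clear assignment of tests.

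Three stronger readings are tempting, and the documents do not support them.

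- A reader might infer that the plan will overstate the five-year gain. That follows only from using unpaired tests across visits, which section 4.1 does not assign. The first planned paper (section 4.4) runs to three years, where the excess would be smaller.
- A reader might infer that complete-case ANOVA would lose most survivors and fall below the required 63. The first part depends on independent return at about 85%; with clustering, more than half can remain. The second uses the wrong yardstick, since 63 fits an unpaired per-group number. Even with 52 complete cases and a standard error of 2.88, power for 10 points is about Φ(10/2.88 − 1.96) = 93%.
- A reader might infer that survivors' change has been shown to differ from that of all recipients. The simulation gives everyone the same change, so it cannot show this.

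The absence of a death or non-return rule and of a test-to-comparison map would, alone, be missing detail.

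**Conclusion.** The concern holds in a limited form. For a repeated-measures aim, section 4.1 lists only methods that discard partly observed patients or, if used across visits as unpaired tests, mix survival with change. A better method is available at little cost.

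The gain is large against complete-case ANOVA (about half the variance, under independent 85% return) and small against paired tests (4-12%). Protection against unpaired use is worth about 1-4 points at year 5 if death is related to GH (SD 20, survival 64-80%).

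Return rates, within-patient correlation and the link between GH and death are assumptions. The 64% survival comes from patients over 70, while the cohort starts at 65.

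**What to change.** In the Statistics paragraph of section 4.1:

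1. Analyse change in GH and the other scales with a linear mixed model for repeated measures: categorical time, a stated covariance, and the scheduled post-transplant scores. Name one pre-transplant form as baseline, for example the last before transplantation, since waiting-list forms vary in number and timing. Fit the model among recipients alive at the visit concerned; fitted to all recipients, it extrapolates beyond death and was off by 0.6-1.1 points in the simulation. Report it beside the paired t-test at 1, 3 and 5 years, both labelled as change in survivors to that visit.
2. Do not use unpaired tests or one-way ANOVA across visits in the same patients. Keep between-person tests for the age-matched cohort and for dialysis versus transplanted. State who is in each group and, where patients contribute to both (214 of 289 were transplanted), use a model that allows for it.
3. Use linear, not logistic, regression when a continuous score is the outcome.
4. Beside each estimate, give the deaths, the number of patients used, and the return rate among those alive.

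The cost is wording and modest extra analysis, with no new data. The model assumes that unreturned forms are missing at random; the 0.2-0.4 point error when return depends on usual GH is the reason to keep the paired test.
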